4.2.2.1 Pembrolizumab Dose Modifications

See the table below for Dose Modification guidelines for pembrolizumab.

Table 3: Dose modification and toxicity management guidelines for immune-related AEs associated with pembrolizumab monotherapy and IO Combinations

General instructions:
 
 1. Severe and life-threatening irAEs should be treated with IV corticosteroids followed by oral steroids. Other immunosuppressive treatment should begin if the irAEs are not controlled by corticosteroids. 2. Study intervention must be permanently discontinued if the irAE does not resolve or the corticosteroid dose is not \leq10 mg/day within 12 weeks of the last study intervention treatment. 3. The corticosteroid taper should begin when the irAE is \leq Grade 1 and continue at least 4 weeks. 4. If study intervention has been withheld, study intervention may resume after the irAE decreased to \leq Grade 1 after corticosteroid taper. 				
--	--	--	--	--

irAEs	Toxicity Grade (CTCAE v5.0)	Action With Pembrolizumab	Corticosteroid and/or Other Therapies	Monitoring and Follow-up
Pneumonitis	Grade 2	Withhold	
 • Administer corticosteroids (initial dose of 1 to 2 mg/kg prednisone or equivalent) followed by taper 	
 • Monitor participants for signs and symptoms of pneumonitis
	Recurrent Grade 2, Grade 3 or 4	Permanently discontinue	
 • Add prophylactic antibiotics for opportunistic infections 	
 • Evaluate participants with suspected pneumonitis with radiographic imaging and initiate corticosteroid treatment
Diarrhea/Colitis	Grade 2 or 3	Withhold	
 • Administer corticosteroids (initial dose of 1 to 2 mg/kg prednisone or equivalent) followed by taper 	
 • Monitor participants for signs and symptoms of enterocolitis (ie, diarrhea, abdominal pain, blood or mucus in stool with or without fever) and of bowel perforation (ie, peritoneal signs and ileus)
	Recurrent Grade 3 or Grade 4	Permanently discontinue		
 • Participants with \geqGrade 2 diarrhea suspecting colitis should consider GI consultation and performing endoscopy to rule out colitis

irAEs	Toxicity Grade (CTCAE v5.0)	Action With Pembrolizumab	Corticosteroid and/or Other Therapies	Monitoring and Follow-up
				
 Participants with diarrhea/colitis should be advised to drink liberal quantities of clear fluids. If sufficient oral fluid intake is not feasible, fluid and electrolytes should be substituted via IV infusion
AST or ALT Elevation or Increased Bilirubin	Grade 2 ^a	Withhold	
 Administer corticosteroids (initial dose of 0.5 to 1 mg/kg prednisone or equivalent) followed by taper 	
 Monitor with liver function tests (consider weekly or more frequently until liver enzyme value returned to baseline or is stable)
	Grade 3 ^b or 4 ^c	Permanently discontinue	
 Administer corticosteroids (initial dose of 1 to 2 mg/kg prednisone or equivalent) followed by taper 	
T1DM or Hyperglycemia	New onset T1DM or Grade 3 or 4 hyperglycemia associated with evidence of β -cell failure	Withhold ^d	
 Initiate insulin replacement therapy for participants with T1DM Administer antihyperglycemic in participants with hyperglycemia 	
 Monitor participants for hyperglycemia or other signs and symptoms of diabetes
Hypophysitis	Grade 2	Withhold	
 Administer corticosteroids and initiate hormonal replacements as clinically indicated 	
 Monitor for signs and symptoms of hypophysitis (including hypopituitarism and adrenal insufficiency)
	Grade 3 or 4	Withhold or permanently discontinue ^d		
Hyperthyroidism	Grade 2	Continue	
 Treat with nonselective beta-blockers (eg, propranolol) or thionamides as appropriate 	
 Monitor for signs and symptoms of thyroid disorders
	Grade 3 or 4	Withhold or permanently discontinue ^d		

irAEs	Toxicity Grade (CTCAE v5.0)	Action With Pembrolizumab	Corticosteroid and/or Other Therapies	Monitoring and Follow-up
Hypothyroidism	Grade 2, 3 or 4	Continue	
 Initiate thyroid replacement hormones (eg, levothyroxine or liothyronine) per standard of care 	
 Monitor for signs and symptoms of thyroid disorders
Nephritis: grading according to increased creatinine or acute kidney injury	Grade 2	Withhold	
 Administer corticosteroids (prednisone 1 to 2 mg/kg or equivalent) followed by taper 	
 Monitor changes of renal function
	Grade 3 or 4	Permanently discontinue		
Neurological Toxicities	Grade 2	Withhold	
 Based on severity of AE administer corticosteroids 	
 Ensure adequate evaluation to confirm etiology and/or exclude other causes
	Grade 3 or 4	Permanently discontinue		
Myocarditis	Grade 1	Withhold	
 Based on severity of AE administer corticosteroids 	
 Ensure adequate evaluation to confirm etiology and/or exclude other causes
	Grade 2, 3 or 4	Permanently discontinue		
Exfoliative Dermatologic Conditions	Suspected SJS, TEN, or DRESS	Withhold	
 Based on severity of AE administer corticosteroids 	
 Ensure adequate evaluation to confirm etiology or exclude other causes
	Confirmed SJS, TEN, or DRESS	Permanently discontinue		
All Other irAEs	Persistent Grade 2	Withhold	
 Based on severity of AE administer corticosteroids 	
 Ensure adequate evaluation to confirm etiology or exclude other causes
	Grade 3	Withhold or discontinue based on the event ^e		
	Recurrent Grade 3 or Grade 4	Permanently discontinue		

^aAE(s)=adverse event(s); ALT= alanine aminotransferase; AST=aspartate aminotransferase; CTCAE=Common Terminology Criteria for Adverse Events; DRESS=Drug Rash with Eosinophilia and Systemic Symptom; GI=gastrointestinal; IO=immuno-oncology; ir=immune related; IV=intravenous; SJS=Stevens-Johnson Syndrome; T1DM=type 1 diabetes mellitus; TEN=Toxic Epidermal Necrolysis; ULN=upper limit of normal.

Note: Non-irAE will be managed as appropriate, following clinical practice recommendations.

irAEs	Toxicity Grade (CTCAE v5.0)	Action With Pembrolizumab	Corticosteroid and/or Other Therapies	Monitoring and Follow-up
^a				
^a			AST/ALT: >3.0 to 5.0 x ULN if baseline normal; >3.0 to 5.0 x baseline, if baseline abnormal; bilirubin: >1.5 to 3.0 x ULN if baseline normal; >1.5 to 3.0 x baseline if baseline abnormal	
^b				
^b				AST/ALT: >5.0 to 20.0 x ULN, if baseline normal; >5.0 to 20.0 x baseline, if baseline abnormal; bilirubin: >3.0 to 10.0 x ULN if baseline normal; >3.0 to 10.0 x baseline if baseline abnormal
^c				
^c				AST/ALT: >20.0 x ULN, if baseline normal; >20.0 x baseline, if baseline abnormal; bilirubin: >10.0 x ULN if baseline normal; >10.0 x baseline if baseline abnormal
^d				The decision to withhold or permanently discontinue pembrolizumab is at the discretion of the investigator or treating physician. If control achieved or ≤ Grade 2, pembrolizumab may be resumed.
^e				Events that require discontinuation include, but are not limited to: encephalitis and other clinically important irAEs (eg, vasculitis and sclerosing cholangitis).

Dose modification and toxicity management of infusion-reactions related to pembrolizumab

Pembrolizumab may cause severe or life threatening infusion-reactions including severe hypersensitivity or anaphylaxis. Signs and symptoms usually develop during or shortly after drug infusion and generally resolve completely within 24 hours of completion of infusion. Dose modification and toxicity management guidelines on pembrolizumab associated infusion reaction are provided in

When study interventions are administered in combination, attribution of an adverse event to a single component is likely to be difficult. Therefore, while the investigator may attribute a toxicity event to Pembrolizumab or combination, For adverse events listed, both interventions must be held according to the criteria in the Dose Modification and Toxicity Management Guidelines for Immune-Related Adverse Events Associated with Pembrolizumab table.

Holding Study Interventions:

When study interventions are administered in combination, if the AE is considered immune-related, both interventions should be held according to recommended dose modifications.

Restarting Study Interventions:

Participants may not have any dose modifications (no change in dose or schedule) of pembrolizumab in this study, as described in [Table 6].

If the toxicity does not resolve or the criteria for resuming treatment are not met, the participant must be discontinued from all study interventions.

If the toxicities do resolve and conditions are aligned with what is define then treatment may be restarted at the discretion of the investigator.[In these cases where the toxicity is attributed to Pembro or the combination, re-initiation of pembrolizumab as a monotherapy may be considered at the principal investigator's discretion.

Table 4: Pembrolizumab Infusion Reaction Dose modification and Treatment Guidelines

NCI CTCAE Grade	Treatment	Premedication at Subsequent Dosing
Grade 1 Mild reaction; infusion interruption not indicated; intervention not indicated	Increase monitoring of vital signs as medically indicated until the participant is deemed medically stable in the opinion of the investigator.	None
Grade 2 Requires therapy or infusion interruption but responds promptly to symptomatic treatment (e.g., antihistamines, NSAIDs, narcotics, IV fluids); prophylactic medications indicated for ≤24 hrs	
Stop Infusion.
 
Additional appropriate medical therapy may include but is not limited to:
 
IV fluids Antihistamines NSAIDs Acetaminophen Narcotics
 
Increase monitoring of vital signs as medically indicated until the participant is deemed medically stable in the opinion of the investigator.
 
If symptoms resolve within 1 hour of stopping drug infusion, the infusion may be restarted at 50% of the
	
Participant may be pre-medicated 1.5h (\pm 30 minutes) prior to infusion of pembrolizumab with:
 
Diphenhydramine 50 mg po (or equivalent dose of antihistamine).
 
Acetaminophen 500-1000 mg po (or equivalent dose of analgesic).

	
original infusion rate (e.g. from 100 mL/hr to 50 mL/hr). Otherwise dosing will be held until symptoms resolve and the participant should be premedicated for the next scheduled dose.
 
Participants who develop Grade 2 toxicity despite adequate premedication should be permanently discontinued from further study drug treatment
	

Grades 3 or 4
 
Grade 3:
 
Prolonged (i.e., not rapidly responsive to symptomatic medication and/or brief interruption of infusion); recurrence of symptoms following initial improvement; hospitalization indicated for other clinical sequelae (e.g., renal impairment, pulmonary infiltrates)
 
Grade 4:
 
Life-threatening; pressor or ventilatory support indicated
	
Stop Infusion.
 
Additional appropriate medical therapy may include but is not limited to:
 
Epinephrine** IV fluids Antihistamines NSAIDs Acetaminophen Narcotics Oxygen Pressors Corticosteroids
 
Increase monitoring of vital signs as medically indicated until the participant is deemed medically stable in the opinion of the investigator.
 
Hospitalization may be indicated.
 
**In cases of anaphylaxis, epinephrine should be used immediately.
 
Participant is permanently discontinued from further study drug treatment.
	
No subsequent dosing

Appropriate resuscitation equipment should be available at the bedside and a physician readily available during the period of drug administration.
 
For further information, please refer to the Common Terminology Criteria for Adverse Events v4.03 (CTCAE) at http://ctep.cancer.gov
		

Proprietary Information of MD Anderson

4.2.3 SRT and Dose Interruptions

If a patient requires SRT for brain for a single episode of brain progression in \leq 5 brain metastases, treatment with study drug will be interrupted as specified in Section 4.3.1.1. The protocol specified steroid treatment and taper (\leq 16 mg dexamethasone PO daily tapered in \leq 4 weeks four week steroid) must be completed before treatment with the study drugs is resumed.

The length of dose delay/dose interruptions for patients receiving SRT is counted from the date of the last dose of study drug. Patients may resume treatment with study drug after the protocol allowed limit of 6 weeks, if approved by the Investigator. Prior to re-initiating treatment in a subject with a dosing interruption lasting $>$ 6 weeks for any reason including on study treatment with SRT, the PI must be consulted.

4.2.4 Treatment beyond Progression

Study treatment may be continued beyond progression per RECIST v1.1 if pseudoprogression due to the effects of immunotherapy is suspected to have occurred or if disease progression is limited to \leq 5 intracranial lesions that can be controlled with stereotactic radiotherapy (SRT). Clinically stable patients who have a favorable benefit-risk ratio may continue study treatment beyond progression per RECIST v1.1 for either reason if all of the following criteria are met:

- Clinically stable patient with evidence of clinical benefit and favorable benefit-risk ratio as determined by the investigator
- Absence of symptoms and signs (including laboratory values, such as new or worsening hypercalcemia) indicating unequivocal disease progression
- No decline in Eastern Cooperative Oncology Group (ECOG) Performance Status that can be attributed to disease progression
- Absence of tumor progression at critical anatomical sites (e.g. leptomeningeal disease) that cannot be managed by protocol-allowed medical interventions
- Documented investigator/patient discussion of treatment options alternative to continuing study treatment at the time of RECIST v1.1-defined disease progression

Study treatment will be discontinued in any patient who continues treatment beyond disease progression per RECIST v1.1 if clinical deterioration because of disease progression occurs at any time or if persistent disease growth is confirmed on follow-up disease assessments performed approximately four weeks later. Post-progression assessments may be conducted sooner if necessary e.g. due to clinical progression. The disease status of patients who continued study treatment and underwent intracranial SRT will be determined by the investigator according to RECIST v1.1 modified by excluding any treated lesions from the sum of largest diameters from baseline onwards.

Proprietary Information of MD Anderson

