2 OBJECTIVES

2.1 PRIMARY OBJECTIVE

To assess clinical benefit rate (CBR), defined as CR + PR + SD > 6 months, in the brain in subjects with MBM per modified RECIST 1.1 criteria who are treatment naïve to anti-PD-1 agents in the metastatic setting (prior adjuvant anti-PD1 allowed. See inclusion and exclusion criteria).

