Subjects will undergo first CNS imaging evaluation at week 6 (\pm 3 days). Subsequently, subjects will be evaluated every 6 weeks (42 days \pm 3 days), independently of any treatment delays, with radiographic imaging to assess response to treatment, until week 30/Cycle 10. Subjects will then undergo imaging evaluation every 12 weeks (84 \pm 7 days). RECIST 1.1 will be used as the primary response rate efficacy endpoint. RECIST 1.1 will be adapted as described in Section 4. to adjust for the tumor response patterns seen with pembrolizumab treatment (e.g., tumor flare), and this adapted/modified RECIST 1.1 will be used by the sites for treatment decisions. The primary response rate efficacy endpoint will be based on independent central review using RECIST 1.1 [1]. Modified RECIST 1.1 will also be used by the local site to determine eligibility and make treatment decisions. MRI of the brain will be the primary radiological method of disease assessment using the RANO-BM criteria.

Subjects may submit an optional tumor tissue sample, if feasible, for biomarker analyses and PDL1 expression evaluation. Subjects with an inadequate archival sample may obtain a new biopsy and subjects with an inadequate newly obtained biopsy may undergo re-biopsy at the discretion of the investigator.

AEs will be monitored throughout the trial and graded in severity according to the guidelines outlined in the National Cancer Institute (NCI) Common Terminology Criteria for AEs (CTCAE) Version 4.03.

Treatment will continue as outlined in Table 1 until documented disease progression, unacceptable AEs, intercurrent illness that prevents further administration of treatment, investigator's decision to withdraw the subject, subject withdraws consent, pregnancy of the subject, noncompliance with trial treatment or procedure requirements, completion of 24 months of treatment with pembrolizumab, or administrative reasons.

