4.4.13 Tumor Imaging and Assessment of Disease

All subjects will undergo CT scanning and volumetric MRI of the brain at the time points specified in the Schedule of Events in Section 5. CT and MRI scans will be assessed locally per the modified RECIST 1.1 criteria. Up to 5 systemic and 5 brain lesions will be followed for efficacy per the criteria.

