Appendix 2: RECIST v1.1

Response Evaluation Criteria in Solid Tumors (RECIST v1.1 Criteria)

The RECIST criteria should be used to assess response to treatment. Only patients with measurable disease should be entered in the study. Measurable extracranial disease is defined as the presence of one lesion that can be accurately measured in at least one dimension (longest diameter to be recorded) as ≥ 2.0 cm with conventional techniques (or as ≥ 1.0 cm by spiral CT). Evaluable lesions should be followed for the assessment of response. Non-measurable lesions include bone lesions, ascites, pleural/pericardial effusion, lymphangitic carcinomatosis, abdominal masses that are not confirmed by CT, and cystic lesions. Disease progression and response evaluations for intracranial and extracranial disease will be determined according to the definitions established in the Response Evaluation Criteria in Solid Tumours (RECIST v1.1). Minor modifications will be applied to the assessment of intracranial lesions:

- General: target lesions should be representative of the subject's baseline tumor burden and should be selected based on their size (i.e. lesions with the longest diameter) and their suitability for accurate repeat assessment.
- Intracranial lesions: (the modifications to RECIST v1.1. impact the number and the minimal size of the target lesions selected at baseline) up to five lesions should be selected as target lesions; all brain lesions in excess of these five target lesions have to be regarded as non-target lesions. Measurable lesions are defined as those that can be accurately measured in at least one dimension with the longest diameter ≥ 5 mm when evaluated with contrast-enhanced MRI. Contrast-enhanced MRI is the only imaging modality accepted for assessment of intracranial lesions.
- Extracranial lesions: up to two lesions per organ representative of all involved organs should be selected as target lesions; the total number of target lesions should not exceed five and all lesions in excess of these five target lesions have to be regarded as non-target lesions.

Baseline Documentation of Intracranial Target and Non-Target Lesions

- All baseline lesion assessments must be performed within 28 days of the first dose of study treatment.

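### After on-study brain radiotherapy (SRT), the criteria for the primary clinical benefit rate are inconsistent, and the lesion-exclusion rule in Section 4.2.4 is not ruled out

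*Combined protocol and SAP*

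**What the plan says.** - **Sections 2.1 and 6.1** score the primary CBR "in the brain in subjects with MBM per modified RECIST 1.1 criteria".
- **Section 6.2.1** promises an estimate with an exact 95% confidence interval for each cohort. It names no response criteria and does not mention SRT.
- **Section 3** states that "RECIST 1.1 will be adapted as described in Section 4. to adjust for the tumor response patterns seen with pembrolizumab treatment", and that "this adapted/modified RECIST 1.1 will be used by the sites for treatment decisions". It then says: "The primary response rate efficacy endpoint will be based on independent central review using RECIST 1.1".
- **Section 4.4.13** says: "CT and MRI scans will be assessed locally per the modified RECIST 1.1 criteria".
- **Section 4.2.4** gives status after on-study SRT to the investigator. The method it prescribes is RECIST v1.1, but "modified by excluding any treated lesions from the sum of largest diameters from baseline onwards".
- **Appendix 2** says its brain modifications "impact the number and the minimal size of the target lesions selected at baseline". PD is a rise in the target sum of at least 20%, and of 5 mm in absolute terms, over the smallest sum on treatment. Irradiated lesions get no exception.
- **Section 2.3** uses nearly the same exclusion to define an exploratory endpoint, radiotherapy-assisted PFS.
- **Sections 4.2.4 and 4.3.1.1** allow SRT for progression in up to 5 brain lesions if the patient is judged to have clinical benefit. To stay on study, the patient must keep one or more target lesions outside the radiation.

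**The concern.** Two texts can claim to be the modified criteria that Sections 2.1 and 6.1 rely on. One is Appendix 2. The other is Section 4, to which Section 3 points, and the explicit change to the RECIST sum found there is the SRT exclusion. Applied to the same scans, they can give opposite values of the primary endpoint. The reader is also unclear: Section 3 gives the primary response endpoint to central review, Section 4.4.13 has scans read locally, and Section 4.2.4 gives status after SRT to the investigator.

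At stake is what CBR measures. If early brain progression is irradiated and then removed from the record back to baseline, local control achieved by radiation is counted as benefit from ipilimumab and pembrolizumab. In an open-label, single-arm study of 25 patients, that choice should not be left until the scans have been seen.

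**Working it through.** **1. The plan's own figure.** Section 6.1 gives n = 25, 16% versus 35%, one-sided 0.10, chi-squared test, power 84%. Using the null variance for the critical value and the alternative variance for power:

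- Power = Φ((0.19 − 1.2816 × √(0.16 × 0.84/25)) / √(0.35 × 0.65/25)) = 0.843, which reproduces 84%.
- Implied cut-off: 25 × (0.16 + 1.2816 × √(0.16 × 0.84/25)) = 6.35, so 7/25. The exact type I error is 0.092 and the exact power 0.827.

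The sample size is not in question.

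**2. One patient under both rules (lesion sizes assumed).** Brain targets are 20, 15, 10 and 10 mm, sum 55. Suppose they are stable at week 6 and the investigator judges that there is clinical benefit. At week 12 (84 days, 2.8 months) they measure 28, 20, 10 and 10 mm, sum 68.

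- Appendix 2: 68/55 = 1.236, a rise of 23.6% and 13 mm. This is PD, so no clinical benefit.
- Section 4.2.4, after SRT to the two growing lesions: the sum is 10 + 10 = 20 mm at baseline and 20 mm at week 12, a change of 0%. If the other two stay stable past 6 months, the patient can count as SD > 6 months.

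**3. Who can take this route.** The patient must have judged clinical benefit, no earlier CR or PR, and growth before 6 months in target lesions that are then irradiated (at most 5). At least one non-irradiated target must remain, and stability must last past 6 months. Clinically stable patients also need a confirmatory scan after 4 weeks (Section 4.3.1.1). Section 4.2.4 changes only the sum of diameters. It does not say that new lesions or non-target progression are disregarded.

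**4. The opposite direction (lesion sizes assumed).** Start again from a sum of 55.

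- The 20 mm lesion shrinks to 2 mm: sum 37, −32.7%, a PR.
- It regrows to 12 mm: sum 47, 47/37 = 1.27, +10 mm, PD. It is then irradiated.
- With that lesion excluded from baseline, the sum was 35 throughout, so there was no PR.
- If the other lesions reach 43 mm (43/35 = 1.229, +8 mm) before 6 months, the patient is a failure. Under Appendix 2 the PR would have counted, if CBR uses best response.

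**5. Size in Cohort A.** One patient is 1/25 = 4 points. Exact (Clopper-Pearson) 95% intervals:

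| Count | CBR | Interval | 16% inside? |
|---|---|---|---|
| 8/25 | 32% | 14.9% to 53.5% | yes |
| 9/25 | 36% | 18.0% to 57.5% | no |

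Exact binomial chances at a true CBR of 16%, if zero, one or two non-benefit patients are counted as benefit in every trial (an assumed range):

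| Observed count | None | One | Two |
|---|---|---|---|
| At least 9/25 | P(X≥9) = 0.012 | P(X≥8) = 0.036 | P(X≥7) = 0.092 |
| At least 7/25 | P(X≥7) = 0.092 | P(X≥6) = 0.200 | P(X≥5) = 0.371 |

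**The case against.** The strongest reply is that the plan already shows what it intends.

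- The sentence in Section 3 that points to Section 4 also assigns the adapted criteria to treatment decisions and ties them to pembrolizumab response patterns such as flare. The next sentence gives the primary response endpoint to central RECIST 1.1 review.
- Section 4.2.4 is headed as treatment beyond progression, refers to progression per RECIST v1.1 as already reached, and never mentions CBR.
- Section 2.3 gives the exclusion an exploratory endpoint of its own, which would be largely redundant if the exclusion governed ordinary scoring.
- Section 4.4.13 goes on to describe following up to 5 brain lesions, which fits Appendix 2 better than Section 4.2.4.

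All of this stands. A reader might infer that the plan instructs sites to count irradiated progression as benefit, or that the two rules are evenly balanced. The documents support neither: read together, they lean towards PD. They do not close the matter, because Sections 2.1 and 6.1 name the modified criteria for the primary endpoint, Section 4.2.4 speaks of disease status without limiting its use, and Section 6.2.1 is silent. Section 3 does state that second-course outcomes are left out of CBR. It has no such sentence for SRT.

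Two other tempting inferences also fail. The bias is not strictly one-way, as step 4 shows. Nor would a reclassified patient overturn a trial decision, since neither 7/25 nor 9/25 is stated as a success rule and Section 6.2.1 is an estimation plan.

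**Conclusion.** The inconsistency is real and touches the primary endpoint, but it is a gap in an otherwise discernible intent, not an instruction to miscount. If the Section 4.2.4 rule were applied to CBR, the error would mainly favour the regimen. Each affected Cohort A patient is worth 4 points, and one patient is enough to decide whether the planned interval excludes 16%. The stated 84% power is unaffected.

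This rests on two assumptions: that a CR or PR before the progression counts under Appendix 2, and that reclassification happens at all. The route is narrow and the documents give no rate for it, so the tail probabilities show sensitivity and are not a forecast. Settling the rule before the data are read is worthwhile because the change is small and the endpoint is primary.

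**What to change.** In Section 6.2.1, state that CBR is scored by Appendix 2 without the SRT exclusion. Brain progression that meets Appendix 2 before on-study SRT is PD at that scan, and a CR or PR already achieved still counts. In Section 4.2.4, confine the lesion exclusion to treatment decisions and the exploratory radiotherapy-assisted PFS. A CBR sensitivity analysis using the exclusion can be added if the sponsor wants to show both.

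The cost is a few sentences, with no new scans, no new patients and no change to n = 25. Observed CBR may be slightly lower. The documents do not say how the 16% historical control was scored, so the rule may be conservative if that control allowed rescue by SRT.
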